#### 11.4.1 Expected Adverse Events Related to Disease Progression

Subjects enrolled under this clinical protocol are expected to present clinically with adverse events related to natural progression of the disease. The draft guidance entitled "Duchenne Muscular Dystrophy Developing Drugs for Treatment over the Spectrum of Disease" (http://www.parentprojectmd.org/site/DocServer/Guidance\_Document\_Submission\_-Duchenne\_Muscular\_Dystrop.pdf?docID=15283) provides the basis of expected disease-related adverse events.

Adverse events determined to be due to the underlying disease progression will be recorded but will not be subject to the expedited reporting requirements outlined in Section 11.3.2. All AEs related to the disease and unrelated to the gene therapy administration will be reported annually to the FDA and IRB.

# 11.4.2 Anticipated Adverse Event Lab Findings related to Intervention

- Asymptomatic elevations in transaminases are a feature of Duchenne muscular dystrophy, as they are related to release of AST and ALT from muscle tissue and correlate with levels of creatine kinase. These are a feature of the disease itself. Levels of AST (up to 12.3X the upper limit of normal) and ALT (up to 22.6X the upper limit of normal) are expected to be seen at baseline, and in the setting of normal GGT function are not indicative of muscle injury. They are thus not exclusionary for enrollment, and will not be recorded as adverse events prior to gene transfer.
  - Following gene transfer, transient transaminases (up to levels of 2.5x the subject's baseline value) with preserved liver synthetic function and no significant elevation in GGT are anticipated, and will be recorded as Grade 1 adverse events, but not considered as adverse reaction in the presence of a normal GGT value. Mild decreases in leukocytes and lymphocyte counts within the first 30 days after gene transfer have been observed in other trials of AAV mediated gene transfer. Such transient decreases in lymphocytes or leukocytes will be recorded as adverse events but considered anticipated.
- Leukocytosis and neutrophilia during prednisone or prednisolone treatment: An elevation of up to 5000 cells/mm^3 above the subject's baseline value is expected in the neutrophil count (the primary granulocyte in circulation) and, consequently, in the leukocyte count within 5 hours of initiating prednisone or prednisolone therapy, based upon studies in healthy adult volunteers. This occurs secondary to release of granulocytes from the marginated pool into the circulation accompanied by an increase in the size of the marginated granulocyte pool due to steroids. This steroid effect may be seen with increased steroid dosing.

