#### Exclusion Criteria

- 1. Active viral infection based on clinical observations.
- 2. Symptoms or signs of cardiomyopathy, including:
  - a. Dyspnea on exertion, pedal edema, shortness of breath upon lying flat, or rales at the base of the lungs
  - b. Echocardiogram with ejection fraction below 40%
- 3. Serological evidence of HIV infection, or Hepatitis B or C infection
- 4. Diagnosis of (or ongoing treatment for) an autoimmune disease
- 5. Persistent leukopenia or leukocytosis (WBC  $\leq$  3.5 K/ $\mu$ L or  $\geq$  20.0 K/ $\mu$ L) or an absolute neutrophil count < 1.5K/ $\mu$ L
- 6. Concomitant illness or requirement for chronic drug treatment that in the opinion of the SI creates unnecessary risks for gene transfer
- 7. AAV9 binding antibody titers  $\geq 1:400$  as determined by ELISA immunoassay
- 8. Abnormal laboratory values in the clinically significant range in Table 7, based upon normal values in the Nationwide Children's Hospital Laboratory

Table 7: Normal and abnormal laboratory values at Nationwide Children's Hospital Laboratory

System	Assay	Normal Range	Abnormal (Clinically Significant)
Liver Function	GGT	8-80 U/L	>80 U/L
	Total Bilirubin	0.1-1 mg/dL	≥3 mg/dL
	Direct Bilirubin	<0.6 mg/dL	>2 mg/dL
Renal Function	Cystatin C	0.3-1.3 mg/dL	>1.8 mg/dL
Hematologic Hemoglobin		(g/dL) 2 – 6 yrs: 11.5-13.5 6 – 12 yrs: 11.5-15.5	For all ages: $\leq 8 \text{ or } \geq 18 \text{ g/dL}$
		13-18 years: 13-15	-

Hematologic	White Blood Cells	4 – 6 yrs: 5.5-15.5 6 – 10 yrs: 5-14.5 10 – 21 yrs: 4.5-13.5	For all ages: White blood cell count $\leq 3.5 \text{ or } \geq 20 \text{ x } 10^3$ cells/mL OR Absolute neutrophil count of $\leq 1.5 \text{ x } 10^3 \text{ cells/mL}$
-------------	----------------------	--	--

\* For Hemoglobin, subjects will be excluded if they have a value less than the lower limit of normal for age at screening regardless of age. Abnormal but not clinically significant hemoglobin levels may be repeated during the screening period, and the subject accepted for enrollment if the results are not less than the lower limit of normal.

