#### 9.1.2 Gene Transfer Visit

#### 9.1.2.1 Pre Infusion Visit (Day -1)

Subjects will arrive at the Nationwide Children's Hospital within 24 hours prior to gene transfer.

The following assessments will occur at this visit:

- Medical history
- Concomitant Medications
- Adverse Events
- Physical Exam
- Vital Signs (heart rate, respiratory rate, temperature, blood pressure, height (see Section 10.5 for more details) and weight)

The following blood lab work will occur at this visit:

- Complete blood cell count (CBC) and differential, platelets
- Aspartate aminotransferase (AST)/alanine transaminase (ALT)
- Gamma-glutamyl transpeptidase (GGT)\*
- A Comprehensive Metabolic Panel (CMP) that includes:
  - o Albumin/Serum total protein
  - o Serum total bilirubin
  - Electrolytes
  - o Calcium
  - o Creatinine/Blood Urea Nitrogen (BUN)
  - o Serum glucose
  - Alkaline phosphatase
- Prothrombin time (PT)/activated partial thromboplastin time (PTT)/INR
- Creatine kinase (CK)
- Direct Bilirubin
- ELISpots for T-cell responses to AAV9 and Dystrophin
- Whole blood for biobanking

In previous gene therapy studies at NCH, there has been an observed antigen specific T-cell response to the AAV vectors. This is an expected response between 2 - 4 weeks following gene transfer. One possible consequence to such antigen specific T-cell responses is clearance of the transduced cells and loss of transgene expression. All subjects (ages 4 years and older) will already be on prednisone, prednisolone, or deflazacort for 12 weeks at time of enrollment as part of the inclusion criteria. The standard clinical dose of prednisone or prednisolone is 0.75 mg/kg/day, and the standard clinical dose of deflazacort is 0.9 mg/kg/day. In order to dampen the host immune response to our AAV-based therapy, for each subject the glucocorticoid dose will be increased to prednisone or prednisolone 1.0 mg/kg/day, not to exceed 60 mg/day; subjects on deflazacort at enrollment will be placed on prednisone or prednisolone for the immediate perinijection period. For subjects younger than 4 years of age who may not be on a corticosteroid,

\* For subjects taking drugs that potentially induce GGT synthesis through the cytochrome P450 system, the clinically significant range will be estimated starting at two times the levels obtained from the baseline screening test and up.

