## 11.1 Adverse and Serious Adverse Event

## 11.1.1 Definition of an Adverse Event

As stated above this protocol will follow the final regulations issued by the Food and Drug Administration addressing the safety reporting requirements for investigational new drug applications (INDs) found in 21 CFR part 312 and for bioavailability and bioequivalence studies found in 21 CFR part 320. "Safety Reporting Requirements for INDs and BA/BE Studies".

 $\frac{http://www.fda.gov/downloads/Drugs/GuidanceComplianceRegulatoryInformation/Guidances/UCM227351.pdf}{CM227351.pdf}$ 

**Adverse Event (AE)**: Adverse event means any untoward medical occurrence associated with the use of a drug in humans, whether or not considered drug related.

Adverse events will be graded by the investigator accordingly (as indicated in Section 11.4):

- 1 = mild
- 2 = moderate
- 3 = severe
- 4 =life threatening or debilitating
- 5 = fatal

Association or relatedness to the study agent will be graded as follows:

- 5 = unrelated
- 4 = unlikely
- 3 = possibly
- 2 = probably
- 1 = definitely related.

**Adverse reaction:** An adverse reaction means any adverse event caused by a drug. Adverse reactions are a subset of all suspected adverse reactions for which there is reason to conclude that the drug caused the event.

Suspected adverse reaction (21 CFR 312.32(a)) Suspected adverse reaction (SAR) means any adverse event for which there is a reasonable possibility that the drug caused the adverse event. For the purposes of IND safety reporting, 'reasonable possibility' means there is evidence to suggest a causal relationship between the drug and the adverse event. A suspected adverse reaction implies a lesser degree of certainty about causality than adverse reaction, which means any adverse event caused by a drug.

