#### 11.1.2 Unexpected Adverse Events

Unexpected adverse events are those which are not previously reported with recombinant AAV vectors, commonly not seen in association with the subject's underlying disease or with the procedures to be used in this study, or are related to a known toxicity but differ because of greater severity or specificity.

Potential expected AEs include localized injection site reactions, which might also be related to the procedure and be independent of the AAV vector itself. Asymptomatic elevations in transaminases are a feature of Duchenne muscular dystrophy, as they are related to release of AST and ALT from muscle tissue and correlate with levels of creatine kinase. These are a feature of the disease itself. Levels of AST (up to 12.3X the upper limit of normal) and ALT (up to 22.6X the upper limit of normal) are expected to be seen at baseline, and in the setting of normal GGT function are not indicative of muscle injury. They are thus not exclusionary for enrollment and will not be recorded as adverse events prior to gene transfer.

Systemic delivery of AAV vectors have resulted in AEs including asymptomatic transient transaminitis (up to levels of 2.5x the subject's baseline value and 3X the upper limit of normal for DMD subjects for AST and ALT) with preserved liver synthetic function and no significant elevation in GGT) following gene transfer (see Section 11.4.2).

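### Section 11.4.2 denies adverse-reaction status to post-infusion AST/ALT rises because GGT is normal, but GGT is a liver marker and cannot exclude a vector-caused muscle source

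*Combined protocol and SAP*

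**What the plan says.** Section 11.4.2 covers laboratory findings anticipated after the intervention. For the period after infusion it states: "transient transaminases (up to levels of 2.5x the subject's baseline value) with preserved liver synthetic function and no significant elevation in GGT are anticipated". Those that qualify "will be recorded as Grade 1 adverse events, but not considered as adverse reaction in the presence of a normal GGT value". Four conditions therefore apply: the rise is transient, it stays within 2.5 times the subject's own baseline, synthetic function is preserved, and GGT is not significantly raised. The adverse-reaction exemption adds that GGT be normal.

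Other sections bear on the same event:

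- Section 11.1.1: "An adverse reaction means any adverse event caused by a drug".
- Section 11.1.2: "Systemic delivery of AAV vectors have resulted in AEs including asymptomatic transient transaminitis".
- Section 11.2 grades the relationship of events to the study agent, the procedures and the underlying disease on five levels. It makes no exception for any laboratory finding.
- Table 7 (Section 7.1) lists GGT under "Liver Function".
- Section 11.4.2, on why boys with DMD have raised transaminases at baseline: "as they are related to release of AST and ALT from muscle tissue and correlate with levels of creatine kinase". It then says that these baseline levels "in the setting of normal GGT function are not indicative of muscle injury".
- Section 9.1.2.1, on T-cell responses expected two to four weeks after transfer: "One possible consequence to such antigen specific T-cell responses is clearance of the transduced cells and loss of transgene expression".

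**The concern.** Whether the product caused an event is a judgement about that event. Section 11.4.2 replaces the judgement with a laboratory rule for a finding that Section 11.1.2 lists as a known result of the product class. The marker also does not answer the question. A normal GGT argues against a liver source. It says nothing against muscle, the tissue from which the protocol says these enzymes are released in DMD, and CK, which the protocol says moves with them, has no place in the rule.

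What is at stake is attribution. Safety is the only primary outcome, at most three children will be treated, and Section 13 sets out no safety analysis that would correct an attribution fixed beforehand. A rise that the vector did cause could be left out of any account of drug-related events.

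**Working it through.** The plan states no figure for this point, so the check is mainly a comparison of passages.

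**1. Definition against rule.** Under Section 11.1.1 the test for an adverse reaction is causation by the drug. Section 11.1.2 says AAV delivery has produced transient, asymptomatic transaminase rises with preserved synthetic function and no significant GGT elevation, which is the pattern that Section 11.4.2 exempts. The same event is thus a known vector effect in one section and, by rule, not a reaction in the other.

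**2. Can GGT carry the rule?** GGT is a liver test (Table 7), and AST/ALT are described as muscle-derived and tracking CK (Section 11.4.2). A normal GGT removes one possible source and leaves the other open.

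**3. Is the clause needed?** The same paragraph treats transient falls in leukocytes or lymphocytes as adverse events that are anticipated, and stops there. Calling the transaminase rise anticipated would do the same work. The extra clause adds only the denial of attribution.

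**4. Effect on stopping and DLT.** Sections 5.1, 6.5, 11.4 and 11.5 count events that are Grade 3 or higher, unexpected, and at least possibly related; Sections 6.5, 11.4 and 11.5 require two or more in one subject.

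- As written: Grade 1, anticipated, not a reaction. Contribution 0.
- With relatedness graded case by case: Grade 1, anticipated, possibly related. Contribution still 0, because the grade and expectedness tests both fail.
- Even with the grade raised to 3 as well, the event is anticipated. Contribution still 0.

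The DLT note in Section 11.4 exempts these rises as expected. It cites Section 12.4.2; I take this to mean 11.4.2. I read the mention of important laboratory findings in Sections 6.5 and 11.5 as illustrating the counted events, not as a separate trigger.

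**5. How large a rise can be exempted?** Inputs: the 2.5-fold ceiling and the highest baselines expected, AST 12.3 and ALT 22.6 times the upper limit of normal (ULN), all from Section 11.4.2.

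- AST: 2.5 × 12.3 = 30.75 × ULN
- ALT: 2.5 × 22.6 = 56.5 × ULN

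These are the extremes of the expected baseline range, not typical values. Section 11.1.2 adds a second ceiling of three times the upper limit for DMD subjects. If that means three times the same maxima (an assumption), it gives 3 × 12.3 = 36.9 and 3 × 22.6 = 67.8 × ULN, so the 2.5-fold ceiling is the lower one at these baselines.

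**6. Where is CK available?** In Table 8, AST/ALT and GGT are drawn after infusion at 15 scheduled points: Days 1, 7, 14, 30, 45, 60, 75, 90, 120, 150 and 180, two weeks after the steroid return, and Months 12, 18 and 24. CK is drawn at 10 of these. It is not drawn at the five interim draws (Days 45, 75, 120, 150 and two weeks after the steroid return): 15 − 5 = 10.

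**The case against.** The strongest reply is that the label has little practical effect. Adverse reaction is the highest-certainty tier in Section 11.1.1; relatedness is graded separately, and Section 11.4.2 does not forbid grading a rise as possibly related. This partly stands: the Section 11.2 grading still applies on paper. But the two instructions then conflict, most plainly for a rise judged definitely related, and the protocol does not say which prevails.

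A second reply is that AST and ALT are raised in DMD anyway, so a modest rise may be disease. That is a fair reason to grade a given rise as unlikely related. It is not a reason to skip the grading.

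A third is that an immune reaction against muscle would not depend on this label to be noticed. ELISpot is drawn with CK at Days 7, 14, 30, 60, 90, 180 and later, and biopsies follow at Days 90 and 180 and Month 12. That stands. Section 9.1.2.1 also speaks only of transduced cells and loss of expression. That clearance in muscle would raise AST/ALT is an inference, and the point does not rest on it.

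A reader might infer more than the documents support:

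- *That these rises leave the primary safety outcome.* They do not. Section 11.4.2 records them as adverse events, Section 5.1 defines the primary outcome as safety in general, and the DSMB reports in Section 12.1.3 summarise adverse events by severity and list them by participant.
- *That one reclassified child in a cohort of one to three alters 33% to 100% of the safety result.* This presumes an adverse-reaction rate that the plan never defines.
- *That any rise with a normal GGT is exempt.* A persistent rise, one above 2.5 times baseline, or one with impaired synthetic function falls outside the rule.
- *That the muscle-injury remark is the rationale for the post-infusion rule.* It concerns baseline levels. It is a separate inconsistency with the sentence on muscle release shortly before it.

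**Conclusion.** Wrong as written; minor to moderate in severity. For qualifying rises, Section 11.4.2 fixes causality by a marker that cannot exclude a muscle source, against Sections 11.1.1, 11.1.2 and 11.2. The account of drug-related events can therefore understate vector-caused rises, up to the multiples of ULN shown above for a child at the extreme of the expected baseline range. How many events would be affected cannot be worked out from the documents.

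The effect is limited to attribution. Recording of adverse events, DSMB visibility, and stopping and DLT counts are the same with or without the clause. This rests on the two readings given in step 4: the cross-reference to Section 12.4.2 and the mention of important laboratory findings.

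**What to change.** - In Section 11.4.2, delete the part of the quoted sentence that denies adverse-reaction status when GGT is normal, and keep the recording as an adverse event. This also removes the mismatch between GGT not significantly elevated and GGT normal, which can differ for subjects on enzyme-inducing drugs, whose clinically significant range is set from their own baseline.
- Grade the relatedness of each such rise under Section 11.2, and keep it designated as anticipated so that DLT counting does not change.
- Where CK is drawn on the same day (Day 1 and the on-site visits from Day 7), read it with GGT and record the likely source. Do not require this at the five interim draws, which include no CK.
- In Sections 11.1.2 and 11.4.2, reconcile the statement that baseline elevations "in the setting of normal GGT function are not indicative of muscle injury" with the statement that AST and ALT are released from muscle.

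The cost is an amendment to wording. No new test is needed, and no stopping threshold changes. The safety table may show a few more Grade 1 events graded as related.

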#### 11.5 Discontinuation Rules

An independent Data Safety Monitoring Board (DSMB) will be established. Safety data will be monitored on a continual basis throughout the trial. The DSMB can recommend early termination of the trial for reasons of safety. Study enrollment will be halted by the investigators when any subject experiences two or more Grade 3, or higher adverse events that are **unexpected** and **possibly, probably, or definitely related** to the study drug. This will include any subject death, important clinical laboratory finding, or any severe local complication in the injected area related to administration of the study agent. If after review by the DSMB, the decision is made to continue, the study will proceed according to Section 6.4 of this protocol.

The investigators will confer with the DSMB on all Grade 3 or higher adverse events that are possibly, probably, or definitely related to the study agent before continuing enrollment.

## 12 CLINICAL MONITORING

# 12.1 Data and Safety Monitoring Plan

The Data and Safety Monitoring Board (DSMB) will act in an advisory capacity to review participant safety and study progress of Phase I/IIa Systemic Gene Delivery Clinical Trial of scAAV9.U7.ACCA for Exon 2 Duplication-Associated Duchenne muscular dystrophy.

# 12.1.1 DSMB Membership

The DSMB membership consists of persons completely independent of the investigator who have no financial, scientific, or other conflicts of interest with the trial. Current or past collaborators or associates of [name] must note any conflict of interest before their eligibility to serve on the DSMB is approved.

The DSMB will include experts in or representatives of the fields of:

- Pediatric Neurology and Neuromuscular Diseases
- Immunology
- Gene Therapy
- Hepatology
- Muscular Dystrophy Clinical Care
- Clinical Research and Clinical Trials

Individuals invited to serve on the DSMB as either voting or non-voting members must disclose any potential conflicts of interest, whether real or perceived. Conflicts of interest can include professional, proprietary, and miscellaneous interests as described in the NIH Grant Policy Statement and 45 CFR Part 94. Potential conflicts that develop during a member's tenure on a DSMB must also be disclosed. Written documentation attesting to an absence of conflict of interest is required annually.

#### 12.1.2 DSMB Responsibilities

Responsibilities of the DSMB are to:

- Review the research protocol, informed consent documents and plans for data and safety monitoring;
- Evaluate the progress of the trial, including periodic assessments of data quality and timelines, participant recruitment, accrual and retention, participant risk versus benefit, trial site performance, and other factors that can affect study outcome;
- Consider factors external to the study when relevant information becomes available, such
  as scientific or therapeutic developments that may have an impact on participant safety or
  the ethics of the trials;
- Review study performance, make recommendations and assist in the resolution of problems reported by the Sponsor Investigator;
- Protect the safety of the study participants;
- Ensure the confidentiality of the trial data and the results of monitoring; and
- Assist by commenting on any problems with study conduct, enrollment, and sample size and/or data collection.

# 12.1.3 **DSMB** Reporting and Meetings

Reports describing the status of the study will be prepared by the Sponsor Investigator's staff and sent to the DSMB prior to a meeting, or at the DSMB's request.

A meeting (either by teleconference or webcast) with the DSMB will be scheduled prior to study initiation, after the Day 30 visit of the first subject and then approximately every 6 months, or at the DSMB's request. Reports will be submitted prior to a scheduled meeting for review by the DSMB.

Reports will include the following:

- A brief narrative of the study status, including the target enrollment, current and projected time to completing enrollment. Any significant events and/or difficulties should be briefly described in this narrative.
- A brief narrative for each participant describing gender, age, race and ethnicity and other relevant demographic characteristics. The narrative for each participant should briefly describe his/her study status (i.e., dose level, visit number, adverse event information);
- A timeline outlining the study progress relative to visit number for each participant, as well as time points for each SAE/Dose Limiting Toxicity. A total for Adverse Events (AEs) for each participant should be included.
- A summary of AEs by severity levels;
- A listing of AE details grouped by participant;
- A listing of SAE details grouped by participant;
- A listing of deaths
- · A summary of clinically significant laboratory test results

